7.5.6 Overall Survival (OS)

OS is defined as the time from start of study treatment to date of death due to any cause. In the absence of death, OS will be censored at the date the subject is last known to be alive or at the analysis cutoff date, whichever is earlier. Subjects who died after the analysis cutoff date will be censored at the analysis cutoff date. Subject lacking data beyond start of study treatment will have their survival time censored on the date of first dose.

OS will be analyzed using Kaplan-Meier methodology and Kaplan-Meier plots will be provided. The median OS and its two-sided 95% CI will be calculated. In addition, the 6- and 12-month OS rates will be summarized.

7.6 Safety Analyses

The safety analysis set will be used to summarize all safety endpoints.

Adverse events will be coded using Medical Dictionary for Regulatory Activities (MedDRA, Version 20.0 or higher).

Laboratory values will be graded according to the National Cancer Institute (NCI) Common Terminology Criteria for Adverse Events (CTCAE version 4.03 or higher).

Concomitant medications will be coded using World Health Organization (WHO) Drug Dictionary (version: June 2016 or more recent).

7.6.1 Adverse Events

Adverse events (AEs) will be summarized by MedDRA preferred term (PT) in descending frequency of occurrence unless otherwise specified. For incidence reporting, if a subject reports more than one AE that was coded to the same system organ class (SOC) or PT, the subject will be counted only once for that specific SOC or PT.

A treatment-emergent adverse event (TEAE) is defined as a newly occurring or worsening AE after the first dose of study treatment. See [Appendix B](#) for details regarding treatment-emergent classification.

An overall summary of TEAEs will be provided. Summaries of TEAEs by MedDRA classification will also be provided for the following:

- TEAEs
- Grade 3 or higher TEAEs
- Serious TEAEs
- TEAEs leading to dose interruption
- TEAEs leading to dose reduction
- TEAEs leading to treatment discontinuation
- TEAEs leading to death
- Treatment-related TEAEs
- Treatment-related grade 3 or higher TEAEs
- Treatment-related serious TEAEs
- Treatment-related TEAEs leading to dose interruption
- Treatment-related TEAEs leading to dose reduction
- Treatment-related TEAEs leading to treatment discontinuation
- Treatment-related TEAEs leading to death
- TEAEs by SOC, PT and maximum severity. At each SOC or PT, multiple occurrences of events within a subject are counted only once at the highest severity

- TEAEs by SOC and PT

All TEAEs, grade 3 or higher TEAEs, serious TEAEs, TEAEs leading to treatment discontinuation, and TEAEs leading to death will be listed.

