7.7.1.3 Reporting Periods for Adverse Events and Serious Adverse Events

The safety reporting period for all AEs and SAEs is from study Day 1 (predose) through 30 days after the last study treatment. However, all study protocol-related AEs are to be recorded from the time of informed consent. All SAEs that occur after the safety reporting period and are considered study treatment-related in the opinion of the investigator should also be reported to the sponsor.

SAEs will be followed until significant changes return to baseline, the event stabilizes (recovering/resolving) or is no longer considered clinically significant by the investigator, or the patient dies or withdraws consent. All non-serious AEs will be followed through the safety reporting period. Certain non-serious AEs of clinical interest may be followed (including collection of relevant concomitant medications) until resolution, return to baseline, study closure, or the events become chronic to the extent that they are adequately characterized.

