9.3.9.2 Adverse Events

An overview of AEs will provide a tabulation of the incidence of all AEs, treatment-emergent AEs, treatment-related AEs, Grade 3 and higher AEs, SAEs, treatment-related SAEs, deaths, and AEs leading to study treatment discontinuation. Adverse events will be defined as treatment emergent if they are newly occurring or worsened following study treatment.

AEs will be classified by system organ class and preferred term using the Medical Dictionary for Regulatory Activities (MedDRA) and graded using NCI CTCAE, Version 4.03.

The incidence of AEs will be summarized by system organ class, preferred term, severity and relationship to study drug. In the event of multiple occurrences of the same AE in one patient, the AE will be counted once as the occurrence for the maximum grade. AEs leading to premature discontinuation of study drug will be summarized and listed in the same manner.

All AEs will be listed.

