9.3.9.3 Deaths and Serious Adverse Events

SAEs will be listed and summarized in the same manner as all AEs. Events with a fatal outcome will be listed.

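### The SAP limits its general AE tables and listings to treatment-emergent events where the protocol asks for all AEs, SAEs and fatal events, and it gives late treatment-related SAEs no defined flag

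*SAP*

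**What the plan says.** Protocol 9.3.9.2 opens with "An overview of AEs will provide a tabulation of the incidence of all AEs, treatment-emergent AEs, treatment-related AEs". The sentence goes on to Grade 3 and higher events, SAEs, related SAEs, deaths and AEs leading to discontinuation. The section closes with "All AEs will be listed". Protocol 9.3.9.3 adds "SAEs will be listed and summarized in the same manner as all AEs" and "Events with a fatal outcome will be listed".

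On collection, protocol 7.7.1.3 sets the window: "The safety reporting period for all AEs and SAEs is from study Day 1 (predose) through 30 days after the last study treatment". It then extends the window at both ends. Before treatment: "However, all study protocol-related AEs are to be recorded from the time of informed consent". After it: "All SAEs that occur after the safety reporting period and are considered study treatment-related in the opinion of the investigator should also be reported". Protocol 7.7.1.2 has SAEs entered on the CRF as well as on the SAE form.

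SAP 7.6.1 plans an overall summary of TEAEs and a series of MedDRA tables, each for TEAEs or a subset of them. Its listings are these: "All TEAEs, grade 3 or higher TEAEs, serious TEAEs, TEAEs leading to treatment discontinuation, and TEAEs leading to death will be listed". SAP 9.2.1 notes that version 2 moved the AE summaries to a treatment-emergent basis; it does not mention listings. SAP 9.1, on changes from the original protocol, is marked as not applicable.

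SAP Appendix B assigns the TEAE flag. For post-baseline events it gives a rule only when onset is no later than 30 days after the last dose. A closing note sends events of undetermined status into the TEAE summaries and excludes only those found not to be treatment-emergent.

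**The concern.** The protocol names TEAEs as one category beside all AEs, so its all-AE outputs cannot be read as TEAE outputs. The SAP nevertheless replaces each of them with a treatment-emergent subset and does not record this as a departure from the protocol.

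The events at risk are ones the protocol goes out of its way to collect. A serious event that the investigator attributes to the drug, starting after the 30-day window, is reported under a special rule. If the SAP does not say where such an event belongs, the study report may omit it from the AE output, or may count it with events gathered under a different rule. Two programmers following the same SAP could then produce different counts of SAEs and of related deaths.

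**Working it through.** No figure in the plan needs reproducing; this is a comparison of texts and a trace of the flag rules.

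**Step 1: required outputs against planned outputs.**

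| Protocol 9.3.9.2 and 9.3.9.3 | SAP 7.6.1 |
|---|---|
| Overview counting all AEs, with TEAEs as a separate entry | Overall summary of TEAEs |
| Deaths in the overview | TEAEs leading to death |
| Listing of all AEs | Listing of TEAEs |
| SAEs listed and summarised | Serious TEAEs listed and summarised |
| Listing of events with a fatal outcome | Listing of TEAEs leading to death |

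Every row on the right is a restriction of the row on the left.

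**Step 2: events before the first dose.** Take a procedure-related AE that starts between consent and the first dose. If it ended before the first dose date, Appendix B rule a gives N. If it was still present at the first dose, it is a baseline AE and rule b gives N. A later record of the same event can become Y if it worsens, turns serious or turns related, but the pre-dose record stays N. This group therefore leaves the 7.6.1 output with no ambiguity.

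**Step 3: events after the window.** Take a new post-baseline event, not a continuation of a baseline event, and apply the Appendix B rules by days from last dose to onset:

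| Onset (days after last dose) | Within 30 days? | Flag |
|---|---|---|
| 10 | yes | Y |
| 30 | yes | Y |
| 31 | no | none assigned |
| 45 | no | none assigned |
| 90 | no | none assigned |

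Rule a does not apply (the event did not end before first dose), rule b does not apply (it is not a baseline AE), and rule c stops at day 30.

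**Step 4: consequence of a missing flag.** Two readings are open.

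- The 30-day window governs. The event is not a TEAE, and 7.6.1 plans no general table or listing that would hold it.
- The closing note governs. Status is undetermined, so the event enters the TEAE tables. Up to day 30 all AEs are collected; after day 30 the protocol asks only for SAEs judged related. The pooled count then mixes two ascertainment rules.

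The note's own example is an event that cannot be placed as baseline or post-baseline. An event on day 45 is plainly post-baseline, which favours the first reading as the intent, but exclusion is nowhere written. The definition of a TEAE in the body of SAP 7.6.1 has no upper time limit, which points the other way.

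**The case against.** A reader might infer that late treatment-related SAEs have no planned output at all. The documents do not support that. Appendix B never sets such an event to N, and its note, read literally, puts it in the TEAE summaries. SAP 7.6.1.1 summarises serious AEs of special interest without expressly limiting that item to treatment-emergent events, so a late serious skin reaction may appear there. SAP 6.1 submits listings of all clinical data as electronic data sets and keeps only pertinent listings for the report. Deaths up to the cutoff count in overall survival under SAP 7.5.6. Conditions ongoing at baseline are summarised under SAP 7.2, which covers part of the pre-dose group.

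A reader might also try to size the problem from the phase 1 data in protocol 1.6, where 2 of 6 fatal TEAEs among 140 patients were judged drug-related. Those events are not shown to have started after a 30-day window, so they say nothing about late events. Nor do the documents show that delayed toxicity is common: protocol 5.4.3 places severe skin reactions mainly in the first cycle, and 5.4.4 gives no timing for pneumonitis.

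The restriction of the summaries was logged in SAP 9.2.1. Protocol 9.3 describes the SAP as the fuller plan and requires an amendment only when a principal feature changes. Ongoing safety oversight does not depend on these listings: SAEs reach the sponsor within 24 hours and the IDMC reviews expedited SAEs.

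All of this stands, and it rules out the stronger claims. It does not supply the all-AE, SAE and fatal-event listings that the protocol names. Data sets are not report output, survival analysis carries no event term or relatedness, and pneumonitis is not among the AEs of special interest in SAP 7.6.1.1. The log entry covers summaries only, and a fuller plan adds detail; it does not explain dropping named outputs without saying so.

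**Conclusion.** The SAP conflicts with the protocol on AE reporting and should be reconciled with it. What is certain is that the general AE summaries and listings are narrower than protocol 9.3.9.2 and 9.3.9.3 require, and that procedure-related AEs before the first dose fall out of them. What is uncertain is the fate of treatment-related SAEs starting more than 30 days after the last dose: Appendix B leaves them unflagged, and the result is omission or pooling according to the reading.

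No magnitude can be given, because the documents do not report how many such events occurred. The gap concerns the completeness and reproducibility of the safety report. It does not touch the primary efficacy analysis. The conclusion assumes that late related SAEs reach the clinical database, as the CRF instruction in protocol 7.7.1.2 implies.

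**What to change.** - In SAP 7.6.1, add listings of all AEs, all SAEs and all events with a fatal outcome, regardless of TEAE status and with that status as a column. Add a row for all deaths to the overview.
- In Appendix B, state the TEAE flag for onset more than 30 days after the last dose, in line with the 30-day window already there, and make the definition in 7.6.1 agree. Limit the closing note to events that cannot be placed as baseline or post-baseline.
- Show treatment-related SAEs with onset after the window in a separate table or listing, so that they are neither lost nor pooled.
- In SAP section 9, record how the AE summaries depart from the protocol.

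The data are already collected. The cost is SAP wording, a few extra outputs and slightly longer appendices.

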7.6.1.1 Adverse Events of Special Interest

Peripheral neuropathy, corneal events, hyperglycemia, dermatological reactions, and infusion related reactions (IRR) are considered adverse events of special interest (AESI) for enfortumab vedotin. These are medical concepts of composite terms based on the search criteria (standard MedDRA query [SMQ] or sponsor specified query [SSQ]). Other AEs may be added to AESI as necessary. The search criteria for AESI will be maintained in a separate document and finalized prior to final database lock.

Treatment-emergent AESI will be summarized by PT and maximum severity. In addition, serious AESI, treatment-emergent AESI that are related to study drug, leading to dose modification and study treatment discontinuation will be summarized.

For selected AESI, time to onset, improvement, or resolution will be analyzed as appropriate.

Time to onset of a specific AESI will be calculated as time from the first dose of study drug to the start of first treatment-emergent event that meets the respective search criteria. In the analysis of time to onset of AE of a specific grade (e.g., grade 3 or higher), episode of events that are improved from a previous higher grade will not be included.

Resolution is defined as event outcome of ‘recovered/resolved’ or ‘recovered/resolved with sequelae’, or returning to baseline grade as of the latest assessment for conditions that are ongoing at baseline. For events with an outcome of ‘recovered/resolved’ or ‘recovered/resolved with sequelae’, time to resolution will be calculated as time from the event start date to end date. For events that return to baseline grade, time to resolution will be calculated as time from the start of treatment-emergent event to the date the event was last assessed.

For events that are not resolved, improvement is defined as decrease by at least one grade from the worst grade as of the latest assessment. For events that meet the definition of ‘improvement’, time to improvement will be calculated as time from the worst grade of the event to the date the event was last assessed.

Time to onset will be summarized at the subject level. Time to resolution and improvement will be summarized at the event level.

7.6.1.2 Eye examination and Corneal AEs

The data for eye examination (complete eye examination and slit lamp examinations) at baseline and post-baseline visits will be listed. Structural corneal abnormality will be reported by the investigators and corneal events will be identified by the corneal disorders SMQ (narrow scope).

The number and percentage of subjects with slit lamp examination performed at the protocol specified timepoints, the number and percentage of subjects with corneal events at baseline, and the number and percentage of subjects with treatment-emergent corneal events at Cycle 2 Day 22 and Cycle 6 Day 22 will be summarized. In addition, treatment-emergent corneal events will be summarized separately for subjects with and without corneal event at baseline.

7.6.2 Clinical Laboratory Parameters

All laboratory results (hematology and serum chemistry) up to the end of treatment visit will be presented in standardized units. Both observed value and changes from baseline will be summarized with descriptive statistics for each scheduled visit. Shift from baseline to maximum post-baseline NCI CTCAE grade will be summarized for each lab test. Treatment-emergent laboratory abnormalities will also be summarized.

Laboratory results and NCI CTCAE grades for hematology and serum chemistry will be presented in data listings. Normal ranges will be documented and out-of-range values will be flagged. A separate listing of laboratory results with CTCAE grade 3 or higher will be presented.

7.6.2.1 Liver Safety Assessment

The liver safety assessment will be summarized based on the measurements of alkaline phosphatase (ALP), alanine transaminase (ALT), total bilirubin, aspartate transaminase (AST), and their combination as defined below. The number and percentage of subjects meeting the criteria post-baseline will be summarized.

- ALT: > 3xULN, > 5xULN, > 10xULN, > 20xULN
- AST: > 3xULN, > 5xULN, > 10xULN, > 20xULN
- ALT or AST: > 3xULN, > 5xULN, > 10xULN, > 20xULN
- ALP: > 1.5xULN
- Total bilirubin: > 2xULN
- (ALT or AST > 3xULN) and Total bilirubin > 2xULN*
- (ALT or AST > 3xULN) and Total bilirubin > 2xULN and ALP < 2xULN*

*Combination of values measured on the same day or within 1 day apart.

In addition, subjects with the post-baseline liver function test results that are consistent with the Hy's law criteria will be listed.

7.6.3 Electrocardiogram

ECG variables will be summarized with descriptive statistics for each scheduled visit. The number and percentage of subjects with normal and abnormal results for the overall interpretation will be tabulated.

7.6.4 Vital Signs

Vital sign measurements, including heart rate, diastolic and systolic blood pressure, and temperature, will be listed by subject and visit.

7.6.5 Concomitant Medications

Concomitant medications will be summarized by the WHO Drug ATC class and preferred name. The number and percentage of subjects who take concomitant medications will be tabulated. Concomitant medications will be listed by subject. In addition, concomitant medications for treatment of peripheral neuropathy, corneal events, hyperglycemia, rash and IRR will be presented in separate listings.

7.7 Additional Analyses

7.7.1 Patient Reported Outcomes

7.7.1.1 EORTC QLQ-C30

For each QLQ-C30 scale, score will be calculated and missing data will be accounted for according to the EORTC QLQ-C30 scoring manual. Descriptive summary of actual value and change from baseline will be presented by visit using the full analysis set.

The number and percentage of subjects with an improvement of ≥ 10 points from baseline in global health status/QoL scale will be summarized by visit.

The compliance and completion rate of EORTC QLQ-C30 will be summarized for each visit. Compliance rate is defined as the proportion of subjects who completed the instrument among those who are expected to complete at a given visit. Completion rate is defined as the proportion of subjects who completed the instrument among the full analysis set.

7.7.1.2 EuroQol-5D

The EQ-5D health state dimension scores will be converted into a health state index using the time trade-off valuation method and the US-based value set (Shaw 2005). Change from baseline in EQ-5D health state index and visual analogue scale (VAS) will be summarized with descriptive statistics by visit using the full analysis set.

The compliance and completion rate of EQ-5D will be summarized for each visit.

7.7.2 Subsequent Cancer-Related Therapy

The number and percentage of subjects who receive subsequent cancer-related therapies, including palliative radiotherapy, systemic therapy for disease progression, maintenance, and systemic therapy for secondary malignancy, will be summarized for the full analysis set. In addition, time from last dose of study treatment to the first subsequent anticancer therapy and time from last dose of study treatment to the first subsequent systemic therapy for disease progression will be summarized.

7.7.3 Pharmacokinetics

Concentrations of ADC, MMAE, and TAb will be summarized using descriptive statistics (including geometric mean and coefficient of variation) at each PK sampling time point for the PK analysis set. PK parameters will be summarized using descriptive statistics.

Geometric mean estimates of selected PK parameters will be compared as a ratio of drug product manufacturing process (Process B to Process A).

Additional PK and PK/pharmacodynamic analyses may be performed and be presented in a separate report. Data from this study may be combined with data from previous studies for population PK and PK/pharmacodynamic analyses. If performed, these analyses will be described in a separate analysis plan and the results will be reported separately from the CSR.

7.7.4 Antitherapeutic Antibody (ATA)

The ATA incidence rate is defined as the proportion of subjects that develop ATA at any time during the study.

ATA incidence will be summarized by visit and overall using the safety analysis set.

7.7.5 Pharmacodynamic and Pre-treatment Biomarkers

The H-score of Nectin-4 expression at baseline will be summarized with descriptive statistics. Baseline H-score will be displayed in a boxplot by BOR. The number and percentage of subjects with baseline PD-L1 CPS <1 vs. ≥ 1 , and <10 vs. ≥ 10 will be summarized. The TCGA subtype at baseline will be summarized. Additional analyses for pharmacodynamic biomarkers and for pre-treatment biomarkers that are potentially predictive of subject outcomes may be described in a separate analysis plan and the results may be reported separately from the CSR.

8 INTERIM ANALYSIS

Data from Cohort 2 will be analyzed at the timepoints as specified in Sect 6.10.

An IDMC will periodically monitor the trial for safety. The IDMC will review expedited SAEs as they are received. Further details will be provided in the IDMC Charter.

9 CHANGES FROM PLANNED ANALYSES

9.1 Changes from the Original Protocol

Not Applicable.

9.2 Changes from the Original SAP

9.2.1 Version 2 Changes

The SAP was updated to reflect changes in protocol amendments 3, 4 and 5, and add additional details to the analysis. Changes from version 1 are summarized below:

- Sec 2.1, 4, 5, 6.1, 6.2 and 6.10: update per protocol amendments 3, 4 and 5

- Sec 5.3: add efficacy evaluable set for sensitivity analysis of the primary efficacy endpoint
- Sec 6.4.3: update response assessment date algorithm following [Paules 2011](#)
- Sec 6.4.5: add data handling rule for action taken with study treatment of AE
- Sec 6.5 and Appendix C and D: add missing data handling rules for prior therapy and subsequent anticancer therapy dates
- Sec 6.8: update subgroup analysis to those based on important prognostic factors, and clarify subgroup analysis will not be performed for Cohort 2 at the time of the primary analysis of Cohort 1
- Sec 7.2: add summary of pre-existing conditions
- Sec 7.4: update algorithm for duration of treatment
- Sec 7.5.1 and 7.5.2: add definition for time to response; add waterfall plot for maximum percent reduction in sum of diameters
- Sec 7.5.2.1: add analysis to evaluate the concordance between investigator and IRF assessments
- Sec 7.6.1: update AE summary to base on treatment-emergent events only
- Sec 7.6.1.1: add additional details to the analysis of AESI
- Sec 7.6.1.2: add analysis for slit lamp examinations
- Sec 7.6.2: add summary of treatment-emergent laboratory abnormalities
- Sec 7.6.2.1: add liver safety assessment
- Sec 7.6.3: add summary of ECG parameters
- Sec 7.7: move Patient Reported Outcomes, Pharmacokinetics, ATA, and Biomarkers endpoints to ‘Additional Analyses’ section
- Sec 7.7.3: add summary of geometric mean ratio of drug product manufacturing process for selected PK parameters
- Sec 7.7.5: add summary of PD-L1 CPS and TCGA subtype
- Appendix B: update TEAE algorithm to better reflect the definition of TEAEs

